#### 5.2 Numerator for VTR

Fetuses will be regarded as vertically infected if fetal or placental tissue, or amniotic fluid, tests PCR+. Children will be regarded as vertically infected on the basis of IgM or PCR evidence within 7 days of delivery. Infants who lose antibody will be regarded as not vertically infected: this includes infants in whom a falling IgG titer is observed as well as those who become IgG-.

There are reports of children with clinical signs of congenital infection, such as microcephaly, whose mothers were infected in pregnancy, but in whom no laboratory evidence of congenital ZIKV can be obtained from testing serum and CSF for IgM and PCR. Definitions of congenital zika in the absence of laboratory evidence are being developed [2, 3], which may be revised as new data becomes available. Although the evidence is not clear at the time of writing, it seems likely that these infected children will remain IgG antibody positive.

Infants who are IgG antibody positive when last seen may be congenitally infected. The probability that they are congenitally infected depends on two factors: firstly, their age, because maternal antibody declines over time and is usually absent within 15 months. Secondly, the risk of post-natal

Author: [name] (UNIVBRIS)

15

infection. Appendix 5 describes statistical analyses that use data on antibody loss in control children born to IgG+ mothers, and data on post-natal infection on initially IgG- newborns, to estimate the probability of vertical infection in all IgG+ infants whose infection status cannot otherwise be determined.

It remains possible either that congenital infection can take place, causing damage, and clearing prior to delivery and leaving no laboratory markers; or that maternal infection affects fetal development without crossing the placenta. It is for this reason that ZIKA-VT includes a 2nd control group, of children born to mothers with no infection in pregnancy.

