#### 7.1 Vertical transmission rate

Assume that for each woman i we will have estimates of the probability  $\pi_i(t)$  that the onset of her infection occurred in week t. We assume that vertical transmission can only occur if infection exists during pregnancy, so that the *onset* is in the interval  $-2 \le t \le G_i$  where  $G_i$  is the gestational age at delivery. If the probability of vertical transmission given maternal infection at week t is V(t), then the probability of in utero transmission in women i is:

$$v_i = \sum_t V(t)\pi_i(t), \quad Y_i \sim Bern(v_i)$$
(7.1)

The outcome data  $Y_i=0,1$  (1 indicating Vertical infection (VI), 0 indicating no VI in a child born to women i), is a Bernoulli realization of the parameter  $v_i$ . In a Bayesian framework, we can attribute a vague prior to V(t) and use the data obtain posterior distributions for V(t),  $v_i$ , and  $\pi_i(t)$  given the Bernoulli likelihood.

In practice, a smooth parametric or semi-parametric function would be fitted to V(t). The analysis is readily extended to include additional risk factors  $\mathbf{X}_i$  with coefficients  $\boldsymbol{\beta}$ :

$$logit(v_i) = logit(\sum_t V(t)\pi_i(t)) + \boldsymbol{\beta}^T \mathbf{X}_i$$

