## 7.6 Accounting for imperfect test sensitivity and specificity, and cross-reactivity

As noted earlier, we need to calculate for each woman recruited into ZIKA-VT, the probability that she was infected in pregnancy, and the distribution of GA when this infection occurred, if it occurred at all, based on tests with imperfect accuracy.

Author: [name] (UNIVBRIS)

24

For example, a sequence of four ZIKV IgM- results throughout pregnancy, assuming there were no IgG, PCR tests and no symptoms, would be scored as "No evidence of maternal infection in pregnancy" in basic analyses, but there is a possibility that they are all false -ves.

As long as the testing algorithm is relatively sensitive, say 95% or more, the bias in estimates of the vertical transmission due to false -ves is likely to be negligible. A small proportion (<5%) of maternal infections would be missed from the denominator, but their babies will not be followed up, and so would also be missed from the numerator. The exception to this would be if they are not only congenitally infected but their congenital infection is apparent. But it can be shown that, on current evidence, this would lead to only a very slight over-estimation of the VTR.

The difficulties posed by false *positive* IgM tests are, however, far more serious. If the specificity of an IgM test is 95%, then 5% of uninfected mothers will receive false +ve results, and will be considered infected in pregnancy. If 10% of women are infected in pregnancy, then, for every 15 women considered as infected in pregnancy, only (approximately) 10 would be truly infected, and the vertical infection rate will be underestimated by a factor of 1.5. If incidence is lower, and only 1% of women are infected in pregnancy, then only 1 in 5 women being followed are truly infected and the vertical transmission rate will be underestimated by a factor of 5.

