#### 10.2 Missing data

With so many variables, and with so many different analyses, it is difficult to make any general comments on methods for handling missing data. The following comments set out our general approach:

1. In the case of diagnostic test variables, the concept of "missing data" is not applicable: for the purposes of determining whether mothers have been infected in pregnancy, and if so when, the methods are designed to deal with any pattern of test results occurring at any time before, during, and after pregnancy, including no tests at all. A probability distribution will be created for every woman reflecting when maternal infection took place and whether it took place. With regards to vertical infection, the analysis will assign every child a probability of being vertically

Author: [name] (UNIVBRIS)

31

infected, based on test results, which will be 0,1, or a probability determined by the duration of antibody persistence when last tested.

- 2. With regards to explanatory variables, all analyses will be based on a "complete data" analysis, which assumes that data is missing without regard to outcomes.
- 3. Loss to follow-up will be carefully monitored and tabulated in relation to infection status, in both pediatric and maternal follow-up studies.
- 4. For categorical pediatric outcomes, survival analyses will treat loss to follow-up as censored observations. Alongside these analyses, sensitivity to assumptions about informative censoring will be carried out, including examination of the most extreme assumptions, in which (a) all, or (b) no, censored observations are assumed to reach the endpoint

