#### **TABLES**

#### Table 1: Risks of Vertical Transmission and Congenital malformation.

#### **Definitions:**

- 1. Presumed maternal infection based on PCR+, IgM+, Seroconversion or rising IgG titer
- 2. Trimester, most likely trimester based on test dates and persistence
- 3. Vertical infection based on IgM+, PCR+ in cord or sample from newborn < 7days old, or persistent antibody.
- 4. Severe and mild congenital malformation, to be defined

	Trimester of presumed infection	Symptoms during pregnancy	Number of Mothers infected	Number Vertically infected	Number of Congenital malformations (severe)	Number of Congenital malformations (mild)
	1	Yes				
		No				
ZIKV	2	Yes				
		No				
	3	Yes				
		No				
	1	Yes				
		No				
DENV	2	Yes				
		No				
	3	Yes				
		No				
	1	Yes				
		No				
CHIKV	2	Yes				
		No				
	3	Yes				
		No				

Author: [name] (UNIVBRIS)

34

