## APPENDIX 5. Role of Antibody persistence in diagnosis of congenital infection

The criteria for congenital infection (CI) are: PCR+ in serum, urine or CSF OR IgM+ in serum, urine or CSF; OR congenital zika syndrome meeting an agreed definition (see *Section 5.2*) Infants who lose IgG antibody, or who have consistently falling IgG titers, will be regarded as not CI.

The remaining children are those that remain IgG+ at last follow up. They have a probability of being congenitally infected that increases with time, but it is necessary to take into account that they may have acquired antibody following a post-natal infection.

Suppose we have available information on the probability Ab(t) that an uninfected child born to an antibody +ve mother remains IgG+ t weeks after delivery. Suppose also that we have information on the probability Pn(t) that an initially IgG- newborn is IgG+ t weeks after birth as a result of a postnatal infection.

Now consider the babies born to women infected in pregnancy: all will be initially lgG+. The proportion lgG+ at time t is:

$$X(t) = (V + (1-V)Ab(t)) + (1-V-(1-V)Ab(t))Pn(t)$$

If there was no post-natal acquisition of antibody, we should observe X(t) fall off to an asymptote V representing the vertical transmission rate. Instead we expect X(t) to fall until all maternal antibody is lost, and then continue to rise in response to postnatal acquisition. As we can observe Ab(t) and X(t), and we have data on and Pn(t), we can recover an estimate of V.

If AB(t) indicates having IgG antibody at time t, then the probability that a child who is IgG+ at age t is CI is:

$$p(CI \mid AB(t)) = \frac{p(AB(t) \mid CI).p(CI)}{p(AB(t) \mid CI).p(CI) + p(AB(t) \mid \overline{CI}).p(\overline{CI})}$$
$$= \frac{V}{V + (1 - Ab(t))V}$$

These analyses can be extended to include covariates, and can be integrated into the calculation of the vertical transmission rate (Section 7.1) [14].

Data on Ab(t) will be generated from within ZIKA-VT, but we will also refer to other sources of information as listed in the following table, which will be updated regularly:

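### IgM error is modelled for mothers but not for infants, and no rule says whether an early infant IgM+ or later loss of antibody prevails, so the vertical transmission rate can be biased in either direction

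*SAP*

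**What the plan says.** Three places make a positive newborn IgM sufficient for infection.

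- Section 5.2: "Children will be regarded as vertically infected on the basis of IgM or PCR evidence within 7 days of delivery".
- Table 1, definition 3, which also accepts cord samples: "Vertical infection based on IgM+, PCR+ in cord or sample from newborn < 7days old, or persistent antibody".
- Appendix 5: "The criteria for congenital infection (CI) are: PCR+ in serum, urine or CSF OR IgM+ in serum, urine or CSF".

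Section 5.2 then adds a rule pointing the other way: "Infants who lose antibody will be regarded as not vertically infected". It extends this to infants with a falling IgG titer, and Appendix 5 repeats it. Neither place says which rule applies to an infant who meets both.

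In section 7.1 the infant result Y_i is a Bernoulli draw from v_i, with 1 "indicating Vertical infection (VI), 0 indicating no VI in a child born to women" i. No misclassification term appears. Section 10.2, item 1, gives each child a probability of infection "which will be 0,1, or a probability determined by the duration of antibody persistence when last tested".

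For mothers the treatment differs. Section 7.6 illustrates the problem ("If the specificity of an IgM test is 95%, then 5% of uninfected mothers will receive false +ve results"), and Appendix 2 builds a Bayes correction using maternal sensitivity, specificity and cross-reactivity. Section 5 states that test error makes both the numerator and the denominator hard to define. Section 4 lists differences in test sensitivity, specificity and cross-reactivity among the conditions under which estimates must stay unbiased, and asserts that the plan achieves this.

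**The concern.** The infant endpoint rests partly on IgM. Section 5.4 describes the ZIKV–DENV cross-reaction as a property of the available IgM tests, not of testing in mothers. When transmission is uncommon, most infants of infected mothers are uninfected and therefore at risk of a false positive. A model without an infant error term reads each such result as a transmission.

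Three consequences follow.

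- VTR, which section 1.3 calls the most important target parameter, absorbs infant test error.
- The second main outcome, severe damage given vertical infection, is diluted by infants who were never infected.
- Sections 7.4.6 and 7.5.1 use a congenitally infected infant to restrict maternal infection to pregnancy. A false-positive infant can therefore cancel the maternal false-positive correction for that woman. Section 8.2.2 could likewise count her negative tests as failures of sensitivity.

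The same plan is applied to DENV and CHIKV.

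**Working it through.** **The plan's own maternal figures.** With 95% specificity and 100% sensitivity, per 100 women:

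- 10% infected: 10 + 0.05 × 90 = 14.5 flagged, a factor of 1.45. The SAP's approximate 15 and 1.5 agree.
- 1% infected: 1 + 0.05 × 99 = 5.95 flagged, a factor of 5.95, or about 1 in 6. The SAP's 1 in 5 and factor of 5 do not follow from its inputs. This is a side point.

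**Infant inputs.** The SAP gives no newborn sensitivity (Se), specificity (Sp) or VTR (V). The values below are assumptions; 95% is borrowed from the maternal illustration.

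**Truly infected mothers.** Apparent VTR = V·Se + (1 − V)(1 − Sp). With Se = 100%:

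| True V | Sp 95% | Sp 99% |
|---|---|---|
| 1% | 5.95% | 1.99% |
| 5% | 9.75% | 5.95% |
| 10% | 14.5% | 10.9% |
| 20% | 24.0% | 20.8% |
| 30% | 33.5% | 30.7% |

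At V = 10% and Sp = 95%, the true share of infants classed as infected is 0.10/0.145 = 69%. If the other 31% had no severe outcomes, the risk of severe outcome given infection would appear at 69% of its true value.

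**Direction.** The bias is upward only if (1 − V)(1 − Sp) > V(1 − Se). The break-even sensitivity of the whole infant algorithm is 1 − (1 − V)(1 − Sp)/V. At V = 10%:

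- Sp 95%: 1 − 0.9 × 0.05/0.1 = 55%.
- Sp 99%: 1 − 0.9 × 0.01/0.1 = 91%.

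Below these values VTR is under-estimated.

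**All flagged mothers, denominator corrected.** Maternal Sp = 95%, maternal Se = 100%, V = 10%, infant Se = 100%, and PPV = true infections/flagged women. Dividing by PPV stands in for the planned joint model:

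[PPV(V + (1 − V)(1 − Sp)) + (1 − PPV)(1 − Sp)]/PPV.

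- 10% maternal infection, PPV = 10/14.5 = 0.690: at infant Sp 95%, (0.690 × 0.145 + 0.310 × 0.05)/0.690 = 16.8%; at Sp 99%, 11.4%.
- 1% maternal infection, PPV = 1/5.95 = 0.168: at infant Sp 95%, (0.168 × 0.145 + 0.832 × 0.05)/0.168 = 39.3%; at Sp 99%, 15.9%.

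The section 7.4.6 conditioning puts each falsely matched mother–infant pair into the denominator as well, which becomes PPV + (1 − PPV)(1 − Sp). At infant Sp 95% the results are then 16.4% and 31.5%.

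**If antibody loss overrides the early IgM+.** At V = 10%, Sp = 95%, with a share r of false positives reclassified, apparent VTR = 0.10 + 0.045(1 − r):

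- r = 0: 14.5%
- r = 50%: 12.25%
- r = 90%: 10.45%
- r = 100%: 10.0%

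**The case against.** Four arguments limit the point.

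**Antibody loss.** A reader might infer that a newborn IgM+ fixes the child as infected for good. The documents do not support that. Sections 5.2 and Appendix 5 class infants who lose antibody as uninfected, maternal antibody is said to be usually gone within 15 months, and ZIKA-VT follow-up lasts two years (section 3.1). This stands, and could remove most of the bias. It is not a full answer: precedence is unstated, the infant must be followed long enough, and section 10.5 allows estimates to be updated at any time. As worded, the rule would also reclassify a PCR+ infant with a falling titer, although section 5.4 treats PCR as effectively 100% specific.

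**Expert group.** Section 5 gives the group the criteria for vertical transmission, and section 1.2 foresees further tests on stored samples. Newborn error is therefore not ignored. But the group sets maternal criteria too, and the SAP still models maternal error.

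**Direction.** A reader might infer that VTR is necessarily over-estimated. That depends on infant sensitivity, and section 5.2 itself mentions affected children with no IgM or PCR evidence. Persistent IgG may recover some of these, but the sign remains open.

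**Correcting mothers only.** A reader might infer that this always moves VTR further from the truth. It does not. In the SAP's 10-of-15 example with V = 10%:

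- Infant Sp 99%: (10 × 0.109 + 5 × 0.01)/15 = 7.6%; times 1.5 gives 11.4%, which is closer to 10%.
- Infant Sp 95%: (10 × 0.145 + 5 × 0.05)/15 = 11.3%; times 1.5 gives 17.0%, which is further away.

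Table 1 is also limited evidence, since section 6 presents it as uncorrected and warns of bias.

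**Conclusion.** The point holds in a limited form and should be fixed. The SAP acknowledges numerator error and claims unbiasedness, but supplies an error model for mothers only. It also leaves two infant rules in conflict and lets infant status override the maternal timing model.

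The size depends on unknown newborn accuracy. With 100% infant sensitivity, apparent VTR among truly infected mothers is 1.45 times the truth at V = 10% and 5.95 times at V = 1% if specificity is 95%; at 99% specificity the factors are 1.09 and 1.99. Lower infant sensitivity reduces or reverses the bias, and a prevailing antibody-loss rule takes it towards zero. The figures for all flagged mothers rest on a simple divisor and are not outputs of the planned model. What is established is that the plan as written cannot guarantee an unbiased VTR; neither a fixed direction nor a fixed size is.

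**What to change.** 1. In section 7.1, model the observed infant result as P(positive) = Se_inf·v_i + (1 − Sp_inf)(1 − v_i). Use separate priors for PCR (specificity about 1) and for IgM-only positives, with a ZIKV–DENV cross-reactivity term.
2. Carry the resulting infant probability into sections 7.2, 7.4.6 and 7.5.1, and into item 1 of section 10.2, in place of a fixed 1 for IgM-only infants.
3. Reconcile the early-IgM+ and antibody-loss rules in section 5.2 and Appendix 5, stating how an infant who meets both is classified and how PCR+ infants are handled.
4. Show PCR-confirmed and IgM-only vertical infection separately in Tables 1, 3 and 4.
5. Report VTR over a stated range of infant sensitivity and specificity while newborn accuracy data are lacking.

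The cost is SAP wording and a few parameters in a Bayesian model that already carries test-accuracy priors. VTR intervals will be somewhat wider, reflecting uncertainty that the present model leaves out.

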#### 7.5.3 Estimating the persistence distributions of multiple tests

The ZIKA-VT protocol provides for

Author: [name] (UNIVBRIS)

23

- (i) PCR, IgM, and IgG tests on women with symptoms,
- (ii) PCR on all IgM+, IgG seroconversions, and rises in IgG titer.
- (iii) Repeat PCR, IgM, and IgG tests at the prescribed intervals until a first PCR-, IgM-, IgG falling titer, respectively.
- (iv) Use of serum, saliva, and urine samples.
- (v) Avidity tests may be used to determine if an infection is primary or secondary; this also carries information on timing of infection

Thus, each woman's record is likely to consist of a series of results on at least three tests and possibly more if more than one assay of each type is used.

The analysis above for a single test is readily extended to two or more tests k=1,2...K. The data on each individual i now consists of K sets of implied -++- sequences denoted  $U_{Li_k}, U_{Ri_k}, W_{Li_k}, W_{Ri_k}$ , and the parameter set is expanded to accommodate K distributions  $F_k(d,\theta_k)$ . The likelihood for the persistence tests for woman i is then:

$$\Pr\left(\begin{array}{c} (U_{Li_{k}}, U_{Ri_{k}}, W_{Li_{k}}, W_{Ri_{k}}) \mid \pi_{i}(t), \theta_{k} \end{array}\right) = \sum_{t} \pi_{i}(t) \prod_{k} \left( F_{k}(W_{Ri_{k}} - t - 1, \theta_{k}) - F_{k}(W_{Li_{k}} - t - 1, \theta_{k}) \right) \quad Max_{k}(U_{Li_{k}}) \leq t \leq Min_{k}(U_{Ri_{k}})$$

Note that, in this framework, the date of symptoms and the dates of short persistence tests such as PCR, are highly informative about the persistence distributions of longer persistence tests such as IgM and rising IgG.

Extension to multiple tests, use of a variety of tests, and changes in which tests are used, raises questions about the numbers of parameters that may need to be estimated. Our initial strategy will be to assume that the persistence distributions of all tests of the same type (PCR, IgM, rising IgG) have the same underlying parametric or semi-parametric form, with persistence distributions that differ only by a single parameter, for example based on a proportional hazards assumption. This constant would be estimated from the data. Persistence distributions for different *samples* (serum, saliva, urine) on the same test will be treated the same way.

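### A falling IgG titre is scored as no vertical infection, although a truly infected infant's titre will often fall while maternal antibody wanes; the VTR is biased downward

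*SAP*

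**What the plan says.** SAP Section 5.2 defines the VTR numerator. PCR+ fetal or placental tissue or amniotic fluid, or IgM or PCR evidence within 7 days of delivery, makes a case. For exclusion: "Infants who lose antibody will be regarded as not vertically infected: this includes infants in whom a falling IgG titer is observed". No minimum age, size of fall, number of samples or final negative result is required.

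Appendix 5 lists PCR, IgM or an agreed congenital Zika syndrome as positive criteria, then excludes: "Infants who lose IgG antibody, or who have consistently falling IgG titers, will be regarded as not CI".

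Section 10.2, item 1, gives every child a score of vertical infection, "which will be 0,1, or a probability determined by the duration of antibody persistence when last tested". A falling titre therefore enters as 0.

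Three other statements bear on the rule:
- Appendix 5: "Now consider the babies born to women infected in pregnancy: all will be initially" IgG+.
- Section 5.2: "maternal antibody declines over time and is usually absent within 15 months".
- Section 5.2, on infected children without IgM or PCR evidence: "it seems likely that these infected children will remain IgG antibody positive".

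Section 5.2 also says that a child still IgG+ at the last visit could be congenitally infected, with a probability that depends on age and on postnatal risk.

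**The concern.** The exclusion treats a falling titre as equivalent to lost antibody. An infected infant carries waning maternal IgG plus its own, so the measured total can fall while the child never becomes negative. The SAP expects infected children without IgM or PCR evidence to stay positive; it does not say that their titre will hold steady.

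Infants exposed to the error are those infected but lacking PCR, IgM or agreed-syndrome evidence, chiefly where the fall is recorded before maternal antibody has gone. For them a real transmission becomes a 0. That lowers the VTR, which Section 1.3 calls the most important target parameter. It also puts infected children into the comparison cohort with maternal infection but no vertical infection (Section 3.1).

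**Working it through.** The SAP gives no figure on this point, so there is none to reproduce. Four checks follow.

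**1. Does a falling titre separate infected from uninfected infants?**

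From the SAP: all exposed babies start IgG+ (Appendix 5), and maternal antibody is usually gone by 15 months, about 65 weeks (Section 5.2).

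Assumed: maternal titre 1 at birth, decaying exponentially with 4, 6 or 8 halvings in 65 weeks (half-life h = 16.25, 10.8 or 8.1 weeks), and own IgG equal to o times the maternal titre at birth.

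Total(t) = 2^(−t/h) + own(t); fold fall = Total(0)/Total(t). With constant own IgG this is (1 + o)/(2^(−t/h) + o). At h = 10.8, t = 26, o = 0.5: 1.5/(0.189 + 0.5) = 2.18.

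Ranges are over the three half-lives; a value below 1 is a rise.

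| o | Own IgG constant, birth to 26 weeks | Own IgG rising linearly from 0 over 26 weeks, birth to 13 weeks |
|---|---|---|
| 0.1 | 2.6 to 5.3 | 1.6 to 2.6 |
| 0.25 | 2.2 to 3.5 | 1.4 to 2.2 |
| 0.5 | 1.8 to 2.5 | 1.2 to 1.7 |
| 1.0 | 1.5 to 1.8 | 0.93 to 1.20 |

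For comparison, an uninfected infant's titre falls 3.0- to 9.2-fold by 26 weeks. An infected infant's titre falls less, but it still falls in most of these scenarios. It does not always fall: with own IgG rising to 1.5 times the maternal level, the total at 13 weeks is above its birth value.

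The fall also flattens. At h = 10.8 and constant o = 0.5 it is 2.18-fold at 26 weeks, 2.80 at 52 and 2.91 at 65, so only 2.91/2.80 = 1.04-fold between 52 and 65 weeks.

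**2. Do the passages agree?**

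- Section 5.2 needs one observed fall; Appendix 5 needs consistent falls. Before maternal antibody has gone, the stricter wording does not cure the flaw, because waning antibody falls consistently.
- Section 5.2 gives an infant still IgG+ at the last visit an age-dependent probability. If that infant's titre is falling, the same section gives 0.
- Appendix 5 defines Ab(t) and X(t) by IgG positivity. Removing infants on slope first leaves a selected group to which Ab(t) no longer applies.

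**3. What does this do to the VTR?**

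Let q be the share of infected infants with no positive criterion, and r the share of those scored 0 because of a falling titre. With the denominator unchanged, observed/true = 1 − q·r. The SAP gives neither quantity. The last column assumes 1000 infected mothers (the initial target in Section 10.3) and a true VTR of 10%, which is 100 transmissions.

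| q | r | Observed/true | Counted of 100 |
|---|---|---|---|
| 0.1 | 0.25 | 0.975 | 97.5 |
| 0.3 | 0.5 | 0.85 | 85 |
| 0.5 | 0.5 | 0.75 | 75 |
| 0.5 | 1 | 0.50 | 50 |
| 0, or any q | any r, or 0 | 1.00 | 100 |

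**4. Can Appendix 5's probability take these infants as printed?**

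No. V/(V + (1 − Ab(t))V) reduces to 1/(2 − Ab(t)). It is 1 at birth (Ab = 1) and 0.5 when maternal antibody has gone (Ab = 0), whatever V is. The text says that the probability increases with time.

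Bayes' rule without postnatal infection gives V/(V + (1 − V)Ab(t)). At V = 0.1 that is 0.10, 0.18, 0.53 and 1.00 for Ab = 1, 0.5, 0.1 and 0.

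With postnatal infection, Ab(t) is replaced by Ab(t) + (1 − Ab(t))Pn(t). The denominator is then Appendix 5's own X(t), and the probability is V/X(t).

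**The case against.** The best defence has four parts.

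- **The criteria are provisional.** Section 5 is headed as background, and it makes the expert group responsible for the criteria for vertical transmission. That stands as context, but Section 5.2 and Appendix 5 state the rule as settled, so it applies until changed.
- **Titres level off.** Follow-up runs two years, past the 15 months. An infected child with its own IgG would reach a plateau and cease to fall consistently. This stands: the exposure is chiefly in Section 5.2's looser wording and in falls recorded early or in children last seen early.
- **There are other routes to a positive classification.** Fetal or placental PCR and an agreed syndrome definition reduce q. This also stands.
- **Appendix 5 can recover V from X(t) without using slope.** True, but integrating it into Section 7.1 is optional, and Section 10.2 still allows individual zeros.

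Some stronger readings are tempting but not supported:

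- A reader might infer that a newborn PCR+ result could be overturned by a later fall. Appendix 5 lists positive criteria first, then exclusions, then the remaining children, and Section 5.4 treats PCR as effectively fully specific. An explicit precedence statement would only clarify.
- A reader might cite Section 7.5.3, which retests "until a first PCR-, IgM-, IgG falling titer, respectively", as proof that infected infants' titres fall. That passage concerns women.
- A reader might conclude that the bias concentrates in trimesters 1 and 2 and distorts V(t). That carries the maternal IgM duration over to the fetus and assumes that fetal infection coincides with maternal infection. The SAP states neither.
- A reader might attach a figure such as 10 to 60% (q of 0.2 to 0.6 times r of 0.5 to 1). Those inputs are not in the SAP.

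**Conclusion.** The rule is wrong as written. A falling titre in a child who is still IgG+ does not show absence of infection, and scoring it 0 conflicts with the SAP's own treatment of IgG+ infants. Taken alone, the rule biases the VTR downward and contaminates the cohort with maternal but no vertical infection.

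The direction is firm, given that some infected infants lack any positive criterion and that some of these show a fall. The size is unknown. It is zero if q or r is zero, and the illustrative ratios of 0.975 to 0.50 rest wholly on assumed q and r. The titre arithmetic supports saying that an infected infant's titre often falls in the first months, not that it always does.

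**What to change.** - Use identical wording in Section 5.2 and Appendix 5: only conversion to IgG− in a child with no earlier positive criterion counts as not vertically infected.
- Leave infants with a falling titre who are still IgG+ as undetermined, with the Appendix 5 probability.
- First correct that formula to V/(V + (1 − V)Ab(t)), with allowance for postnatal infection as shown above.
- As a clarification, state that PCR, IgM and agreed-syndrome criteria take precedence over later IgG decline.

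The cost is a change to the SAP text and to the classification code. More children, including those lost before seroreversion, will carry a probability instead of 0, so early VTR intervals will be somewhat wider. The results will also depend more on the estimates of Ab(t) and Pn(t).
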